1.14.1 Participants

Cohort study participants with thumb base OA who consented to further contact are eligible for the interview study. Occupational and physiotherapists from all sites who have taken part in delivering care to participants for the study are eligible to take part in the focus groups.

2.14.1 Recruitment

Participants from the cohort study who consented to further contact will be purposively selected to take part in a 1:1 semi-structured interview. They will be chosen to represent a range of characteristics considered important from the engagement work e.g., sex, age, perceived severity of problem, response to treatment, a variety of experience of care (e.g., prescribed a hand splint, attended group education) language, and sociodemographic status. Participants will be interviewed 4-6 months after their baseline appointments, so that they have experienced care and will have a sense of their response to the treatment provided.

All therapists at each site who have been responsible for delivering the care will receive study information and consent forms by email about taking part in focus groups.

3.14.1 Informed consent

Participants who consented to further contact and were purposively sampled and selected for the interview study will be sent a letter of invitation, participant information about the interview study and a consent form. Similarly, all therapists who have been involved in providing treatment for participants will be sent, via the PI at that site, a letter of invitation, participant information about the focus group study and a consent form. Participants and therapists will have the option of responding by a reply slip/ email, asking them to inform the researcher if they are willing to participate. A reminder will be sent out if there is no response after two weeks. Those who are willing to participate will be contacted and scheduled an interview or focus group and informed consent will be completed by phone. As well as returning a consent form, (paper form or online REDCap version) both interviewees and focus group attendees, will also be asked to provide additional verbal recorded consent prior to the start of the interview or focus group. Focus group participants will also be asked to complete a short survey with seven questions, aiming to describe sociodemographic characteristics of the focus group participants, and support equality, diversity and inclusion impact assessment (see TOPS Data Collection Focus Group Form v.1).

4.14.1 Methods: Interview study

Semi structured interviews (1:1) will be used to explore and describe participants' experience of care, these will last approximately one hour. A topic guide for the interviews has been created based on the objectives of the study, a review of the literature and the Theoretical Domains Framework (TDF)⁵⁵. TDF amalgamates theories and constructs related to behaviour change and implementation issues into 14 domains. The topic guide draws on these domains to explore perceptions relating to response to treatment, as well as facilitators and barriers to supportive self-management. The topic guide has been reviewed and amended by our PPIE group and will be refined during data collection

to allow any emerging issues to be explored. The interviews will be conducted by phone, video call, or face to face according to participant preference, and will be undertaken by a researcher with qualitative research training.

5.14.1 Methods: Focus group study

A therapist focus group will explore and generate discussion on the factors that influence the response to treatment of those with thumb base OA. The focus group will last approximately two hours and will use a topic guide that has been developed as described above. The focus group will take place face to face or by video meeting and will be conducted by two researchers with qualitative research training.

Withdrawal criteria

A participant can withdraw from the study at any point. If a participant withdraws consent from the study, their existing data up to the date of withdrawal will remain on file and will be included in the final study analysis.

End of study

The end of the study is defined as the point at which data collection is complete and the study database is locked. All Case Report Forms (CRFs), audio files and transcripts will have been received by the data management team at Keele CTU and any data queries will have been resolved. The (Chief Investigator) CI will notify the Research Ethics Committee (REC) of the end of the study within 90 days of study completion.

Stakeholder involvement and PPIE workshop

The final objective of this study is to generate recommendations to improve care. To support this, it is planned to hold a stakeholder workshop to disseminate the results, presenting the key results for the experience and the outcomes of care, and the nature and the strength of factors influencing the outcome of treatment. Including presenting the results of the quantitative and qualitative data triangulation. If appropriate, discussion will then be guided toward identifying the implications of the results on clinical care, and towards suggestions for improving supported self-management, and ideas for future research.

Clinicians (therapists, GPs, surgeons – who have a particular clinical or research interest in thumb base or hand OA) from the CI's existing networks in the UK will be invited to attend using e-bulletin advertisements and direct e-mail invitations (British Association of Hand Therapists, British Society for Surgery of the Hand OA thumb guidelines group, Local GP practices). Patients from the TOPS

FUNDED BY

NIHR | National Institute for
Health and Care Research

study patients' advisory group, who are familiar with group meetings and the study, and its aims will be invited to attend. Participation will be voluntary, as this is a dissemination and discussion event, rather than research that generates data for analysis, there will be no anticipated requirement for formal informed consent. A record of the key points of the discussions and the ideas for improving care and future research will be taken, with no identifiable information included in the summary produced.

The detailed plan for this workshop and methods used to facilitate the group discussions and develop recommendations will be written up and agreed prior to inviting participants.

15 STATISTICS AND DATA ANALYSIS

Quantitative analysis

Summary of baseline data and flow of patients

The full statistical analysis plan will be written, and agreed prior to analysis, hence only an outline of the analysis is described below. The presentation of data and reporting will be informed by the Strobe statement⁶⁶. The numbers of those examined for eligibility and those included and those completing follow up will be presented with a flow chart. The reasons for non-participation or withdrawal will be presented. Key socio-demographic and health data will be presented and compared between those who do and do not complete the three and six-month follow up. Descriptive statistics will be used for this analysis (frequencies and percentages for categorical data, means and standard deviations for numerical data).

Outcome analysis – descriptive statistics

Descriptive statistics, including 95% confidence intervals where relevant, will be used to estimate:

- Overall outcomes of care at three and six months - the change from baseline in pain, function, participation, pain self-efficacy and health related quality of life; and the proportions classed as responders at each time point.
- The proportions who required additional treatments and what care was provided will be described.
- Summarised scores for perceived quality of care (OA-QI).

Outcome analysis

Linear regression for continuous outcomes will be used to explore the association of selected prognostic factors with outcome (pain and function); logistic regression for binary outcome (OMERACT-OARSI responders). Crude (unadjusted) estimates will be calculated as well as estimates of the strength of associations adjusted for relevant covariates (e.g., age, gender, socioeconomic status, presence of comorbidities, baseline value of the outcome). Results from the interview study will inform the order of prognostic factors to be included in the analysis of the relationship between candidate prognostic factors and outcomes. Model fit will be explored using statistics such as R-squared or C-statistic to estimate predictive value, i.e., how well the prognostic factor can explain variability in outcome over and above demographic variables and baseline pain/function.

Sample size calculation

A total of 150 participants will be recruited and, with an anticipated maximum loss to follow-up of 30%, 105 participants would be retained at 6-months. This sample size will enable the proportion of participants meeting the OMERACT-OARSI responder criteria at 6-months to be estimated with a confidence width of 20% (the difference between the lower and upper bound of a 95% confidence interval). The sample size is derived using the Exact (Clopper-Pearson) method. This calculation assumes that the proportion of participants meeting the OMERACT – OARSI responder criteria is 50% (a worse-case scenario for a sample size calculation) but is also reasonable given that 33% - 44% of participants met these criteria in a trial at 3-months where stepped care was not part of the treatment package ¹⁷. Additionally for the secondary objective of investigating the association of prognostic factors with pain and function outcomes. The sample size calculated above (n=105) allows a difference of 0.05 or more in model R2 to be detected at 80% power and 5% significance in a multiple regression to predict our outcomes of interest e.g., (AUSCAN pain or function) when comparing a model with, and without a single predictor of interest. This assumes an R2 value of 0.3 for the model without the predictor of interest and translates to an effect size (f2) of 0.077 (=0.05/0.65). An R2 value of 0.3 is feasible as, it has been achieved in another study predicting outcome in hand therapy ⁵⁹. The sample size calculations were completed using PASS 2020 software ⁶⁰.

Planned recruitment rate.

It is planned to recruit participants from four study sites that each receive 15-20 referrals per month. From recruitment to a previous study at two of these sites it is estimated that at least 3 participants monthly will consent to the study. With a 14-month recruitment period, a total sample size of 150

consenting participants is considered feasible within the fellowship ($4 \times 3 \times 14 =$ a minimum pool of 168 participants).

Procedure(s) to account for missing or spurious data

The amount of missing data, and the reasons for non-response where given, will be reported. Primary analyses will be based on multiple imputation by chained equations to impute missing data. As a sensitivity analysis, analyses of the primary outcome (AUSCAN) will be re-analysed using only the complete data for comparison⁶⁹.

Qualitative analysis – linked study

Data management and analysis of linked study

The interviews and focus group will be audio-recorded, and field notes will be made following each interview and focus group. Transcriptions will be made ad verbatim; all identifiable information will be redacted. The transcripts will be proofread against the audio-recordings and the notes, and then entered into NVivo data management software.

Thematic data analysis will be undertaken using a framework method⁵⁶. The data will be coded within a preliminary pre-defined thematic framework based on the TDF. Two researchers (VJ & CW) will independently code a subsample of transcripts, meet to discuss overlap and divergence and to refine the framework. They will then independently code a minimum of 5% and discuss overlap and refine the framework until a satisfactory consensus between coders has been achieved, anticipating 10-25% will be dual coded⁵⁷. VJ will then continue to code the remaining transcripts meeting with CW regularly to discuss coding decisions. The patients and therapists involved will be invited to inspect the outcomes of the analysis. Additionally key socio-demographic data will be presented in tabular form to describe the sample selected.

Sample size for linked study

For the interview study, it is estimated that up to 20 participants will be needed. Sample size in qualitative research is difficult to estimate in advance⁵⁸ but will be determined in this study by achieving representation of the selection criteria chosen for purposive sampling, and finding similar themes and meaning arising from interviews, with limited new perspectives (or data saturation).

For the focus group it is estimated that 6-10 therapists will be required, to achieve a range of factors in purposive sampling, and be realistic based on having several staff involved in delivering the study

at each of the four sites⁵⁶. Purposive sampling will select therapists from different sites, and a range of job grades in the NHS.

Triangulation of data

A detailed plan for triangulation and integration of the qualitative and quantitative data sets will be written and agreed prior to all data analysis. The findings from the cohort study quantitative data and the qualitative study will be brought together by listing the key findings from each component of the study to create a convergence coding matrix⁶⁷. The findings will be assessed by the research team (together with patient collaborators) to explore where they agree (convergence), offer complementary information on the same issue (complementarity), appear to contradict (dissonance), or where a finding only emerges in one data type (silence)⁶⁸. TDF domains support the generation of recommendations for patient care. For example, if patients believe that self-management will not help them (TDF domain: beliefs about consequences) then this would point to more patient education on the potential impact of self-management may be required. The results of this aspect of analysis will form an important part of the study results to be presented at the stakeholder involvement and PPIE workshop.

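### The sensitivity analysis the protocol names for missing data does not probe outcome-dependent non-return and leaves out the responder proportion that sets the sample size

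*Protocol*

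**What the plan says.** Under the missing-data heading of Protocol section 15, the primary analyses rest on multiple imputation by chained equations. The section promises to report the amount of missing data and any reasons given for non-response. It then names one sensitivity analysis, in which "analyses of the primary outcome (AUSCAN) will be re-analysed using only the complete data for comparison". No other is named in the protocol.

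The sample size paragraph of the same section sets the retained number: "A total of 150 participants will be recruited and, with an anticipated maximum loss to follow-up of 30%, 105 participants would be retained at 6-months". The target is a different outcome from the one in the sensitivity check. The sample is to allow "the proportion of participants meeting the OMERACT-OARSI responder criteria at 6-months to be estimated with a confidence width of 20" per cent, where width means "the difference between the lower and upper bound of a 95% confidence interval". The method is also given: "The sample size is derived using the Exact (Clopper-Pearson) method".

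Section 13 lists the responder outcome as secondary and builds it from AUSCAN pain, AUSCAN function and a global rating of change. Objective 1 in section 10 asks both for the 6-month changes and for the proportion who respond. Section 15 describes itself as an outline, with a full SAP to be agreed before analysis.

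**The concern.** A sensitivity analysis for missing data is useful when it relaxes the assumption on which the main analysis depends. Chained-equations imputation, as normally run, assumes that people with the same observed data have the same outcome distribution whether or not they return the questionnaire. An unadjusted complete-case mean or proportion ordinarily needs more: that returners and non-returners have the same average outcome without conditioning on anything. Comparing the two shows whether the variables in the imputation model move the estimate. It does not show what happens if people stop returning questionnaires because they did badly, or because they recovered and lost interest.

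Scope is the second problem. Re-analysing AUSCAN does not re-analyse responder status, which also uses the global rating of change and is a different summary.

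This is an uncontrolled cohort, so no comparison arm exists in which a similar bias could cancel. Selective non-return would pass directly into the 6-month response figure, which is to be presented to stakeholders and feed recommendations for care.

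**Working it through.** **Inputs from Protocol section 15:** 150 recruited; maximum loss 30%; 105 retained; assumed responder proportion 50%; 95% Clopper-Pearson interval with full width 20 points; earlier responder proportions of 33% to 44% at 3 months.

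**Assumed, not in the documents:** departures of 10, 20 and 30 points among the missing; losses of 10% and 20% for comparison.

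**1. The plan's own figures.** 150 × (1 − 0.30) = 105. Clopper-Pearson limits at n = 105 and p = 0.5 are 0.401 and 0.599, a width of 0.198 and a half-width of 0.099. The smallest n with width at most 0.20 is 104. The stated figures reproduce.

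**2. Why agreement between the two analyses is uninformative here.** Let d be the fraction missing. The overall proportion is

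p = (1 − d) × p(observed) + d × p(missing).

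Take d = 0.30 and p(observed) = 0.50, and suppose the observed variables do not separate returners from non-returners. Imputation then fills in about 0.50 for the missing and gives about 0.50 overall. The complete-case estimate is also 0.50. If the true proportion among the missing is 0.30, the truth is 0.70 × 0.50 + 0.30 × 0.30 = 0.44. The two analyses agree and both are 6 points too high.

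**3. Size of the shift.** If the true response among the missing is δ below what is imputed, the overall proportion is overstated by d × δ.

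| Loss d | δ = 10 points | δ = 20 points | δ = 30 points |
|---|---|---|---|
| 10% | 1 | 2 | 3 |
| 20% | 2 | 4 | 6 |
| 30% | 3 | 6 | 9 |

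A departure in the other direction understates the proportion by the same amounts.

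**4. Extreme bounds.** With all missing counted as non-responders the proportion is (1 − d) × p(observed). With all counted as responders it is that value plus d.

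| Loss d | 33% observed | 44% observed | 50% observed |
|---|---|---|---|
| 10% | 30% to 40% | 40% to 50% | 45% to 55% |
| 20% | 26% to 46% | 35% to 55% | 40% to 60% |
| 30% | 23% to 53% | 31% to 61% | 35% to 65% |

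The range is always d wide. At 30% loss it spans 30 points, against the 20-point interval the study is sized for.

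**5. Departure that would equal the planned half-width.** 0.099 / 0.30 = 0.33, so about 33 points at 30% loss. At 20% loss, 0.099 / 0.20 gives about 50 points.

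**The case against.** The strongest reply is that this belongs to the SAP. The protocol calls its analysis section an outline and introduces the complete-case analysis as one sensitivity analysis without excluding others. Delta-adjusted analyses are typical SAP content. A reader might infer that nothing in the study will test the imputation assumption. The documents do not support that: the full SAP is not available here and may contain such an analysis. What remains is that the protocol is not silent. It chose a particular check and attached it to AUSCAN.

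A reader might also infer that the responder proportion is unprotected. That too goes beyond the documents:

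- Section 14 provides a second questionnaire, up to three telephone attempts and a final postal form, and the minimum data set contains all three responder components.
- Section 17 adds telephone completion when 20% or more of AUSCAN items are missing.
- Section 15 compares those who do and do not complete follow-up.
- AUSCAN and the global rating are also collected at 3 months, so someone lost only at 6 months can be imputed from earlier values of the same measures.

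These steps should reduce the loss and make the imputation more credible. They do not test whether the people still missing differ in outcome. The completer comparison uses socio-demographic and health data, and reasons for non-response are known only when given.

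Two further objections stand as limits. The complete-case comparison is not empty for the prognostic regressions: complete-case regression can remain valid when missingness depends on covariates but not on the outcome, so the point is confined to the Objective 1 descriptive estimates. And 30% is a maximum, the departures are assumed, and even the largest of them stays just inside the half-width. It is also conventional to attach the named check to the primary outcome, and two of the three responder components are AUSCAN subscales.

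**Conclusion.** The point holds in a limited form. For the Objective 1 mean change and responder proportion, the named comparison cannot detect non-return that depends on the 6-month outcome, and it does not extend to the outcome that determined the sample size. The possible bias is modest to material: up to 9 points for the largest departure considered at maximum loss, comparable with the sampling uncertainty the study was designed to accept, and clearly smaller if loss is 10% to 20%. The confidence interval would not reflect it.

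This conclusion assumes that imputation is run in its usual form, with missingness allowed to depend only on observed data, and that loss comes near the planned maximum. It does not say that the sample size is wrong or that the study's conclusions are unsafe. It says that a better check than the one stated is readily available. It is best labelled a cheap improvement.

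**What to change.** In the SAP, and in the protocol when it is next amended:

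1. Keep the complete-case analysis as a secondary comparison, and extend the sensitivity analysis to the 6-month responder proportion.
2. Add delta-adjusted imputation over a pre-specified grid. Shift imputed 6-month AUSCAN pain and function and, consistently, the imputed global rating of change, then re-derive responder status. Shifting AUSCAN alone would leave the three components inconsistent. A simpler alternative is to shift the imputed log-odds of response directly.
3. Report the estimate and 95% CI at each shift. A tipping point is not suitable, because the protocol sets no threshold for the responder proportion.
4. Optionally, show the proportion with all missing counted as non-responders, labelled as an extreme bound.

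The cost is a few reruns of the imputation code and one more table. No new data are needed and the sample size does not change.

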16 DATA HANDLING

Data collection tools and source document identification

Online/postal self-report questionnaires, clinical data collected on study specific CRFs, audio recordings (of interviews and a focus group) will form the basis of the data collection. A dedicated study database will be developed using REDCap this will be managed by the principal investigator (with support from a Senior Application Developer and a Biostatistician). REDCap is housed on Amazon Web Services (AWS) infrastructure which is managed and maintained by Keele University and will be the final repository for the data collection.

Potential participants are screened by clinicians for eligibility using study specific CRFs. For those not consenting, or ineligible to participate in the study, data will be collected on age, gender, and reason for exclusion (if known). Sites will be given the option of uploading data directly into a database. Data collection, storage and study processes will be managed using Research Electronic Data Capture (REDCap). REDCap is a secure web application for building and managing research databases and online and offline data capture. All potential participants who are assessed for eligibility, and all eligible participants who have completed the consent form will be entered onto the REDCap study database and allocated a unique participant study ID so that only anonymised data are used for

analysis. The unique study numbers will be generated from the study database and allocated to each patient before sending a baseline questionnaire. The number will be made up of site ID followed by a sequence of unique numbers. The study number will be for use on CRFs, other study documents and the electronic database. If a site cannot access REDCap then they will have sets of study paperwork (DCFs and ICFs and questionnaires) with predefined ID numbers printed on them. They can collect data on these and send them to Keele CTU where the data will be entered into REDCap generating a new ID number that includes the paper ID number.

All data used for analysis will be de-identified on a separate database and linkage will only take place via the participant's unique ID number. Names and contact details will be deleted after the data collection phase is completed. Paper-based questionnaires and data collection forms will be sent to the Keele CTU administration team in pre-paid envelopes provided to participants and therapists. Paper-based questionnaires and forms will be date stamped on receipt at Keele CTU. Questionnaires will then be logged as returned on a management database, and the participant's responses entered into the study database on REDCap.

Data handling and record keeping

Questionnaires will include the participant's Study ID plus date of birth and initials to confirm the correct participant's study ID has been provided. Study data, including relevant information from participating patient therapy records, will be recorded on CRFs by clinicians or local research staff who are taking part in the study and will be trained in accordance with the protocol on completing CRFs. Data extracted from therapy records will be linked to the participant's Study ID and to study data attributed to each participant. The study site is responsible for redacting all other personal identifiable data prior to CRFs and any other reports being sent to Keele CTU, where appropriate. Following receipt, Keele CTU will contact the site to resolve any missing or discrepant data queries relating to clinical data in accordance with Keele CTU procedures.

Dictaphone audio recordings will be used to record interviews with participants and the focus group meeting. These will be removed from the Dictaphone at the earliest opportunity. The files will be transferred to a secure drive on the university server, immediately after recording, and deleted from the Dictaphone. Video call interviews also recorded by Dictaphone and treated in the same way.

Recordings will be transcribed via Sponsor approved transcription services only. The transfer of recordings to external transcription services will adhere to the secure transfer of recordings/transcripts procedure specified by the Sponsor. A confidentiality agreement will be put in place to cover this arrangement with the service provider.

FUNDED BY

NIHR | National Institute for
Health and Care Research

Access to the final study dataset & archiving

At the end of the study, archiving of essential study documents at the sites and Keele CTU will be authorised by the sponsor following submission of end of study reports which will be for a minimum of 5 years after the end of the study (5 years as per sponsor request). Destruction of essential documents requires authorisation from the Sponsor.

A record of consent will be held in the local investigator site file. All other data will be held by Keele CTU and will be archived in the designated Keele CTU storage facility, until destruction as outlined in the QMS.

Data sharing agreements

Any subsequent requests for access to the data from anyone outside of Keele CTU (e.g., collaboration, joint publication, data sharing requests from publishers) will follow Keele University's QMS.

The anonymised datasets of quantitative data generated during and/or analysed during the current study will be available to request from [contact]. A data request form must be completed outlining the data requested, the reason for obtaining this data (research question / objective), the timing for when the data is required to be available (start date/end date). The Data Custodian and Academic Proposals (DCAP) committee at Keele will only give approval if the data requested is appropriately suited to answer the research question/objective and that the request fits with the original ethical approval and participant consent and adheres to funder and legal restrictions. Only anonymous data will be available for request in aggregated format or at the level of the individual participant.

